# Statistical Analysis Plan

## Primary Objective

• To compare highest subjective pain score between patients receiving EMLA cream vs. lidocaine for analgesia for vulvar biopsy

#### Exposure

• Patients were randomly assigned with equal probability to receive either EMLA cream or a lidocaine injection for analgesia for vulvar biopsy

## **Primary Outcome**

- Pain was recorded during the application of EMLA cream or injection of lidocaine, and immediately after the biopsy on a 100 mm visual analog scale. If multiple sites were biopsied and the pain level differed between sites, then the highest pain score was recorded. If the anesthesia was inadequate in either treatment arm prior to biopsy, then an additional lidocaine injection was given and pain was recorded prior to the additional injection. The highest of all these pain measurements will be used as the primary outcome.
  - Continuous variable ranging from 0 to 100

## Secondary Objective

• To compare pain scores at vulvar biopsy between treatment arms

## Secondary Outcome

- Pain score at vulvar biopsy measured on a 100 mm visual analog scale
  - Continuous variable ranging from 0 to 100

# Exploratory Objective

• To compare subjects' and providers' perceptions of acceptability and tolerability of the procedure between EMLA cream and lidocaine

# Exploratory Outcomes

- Patient's response to "overall, how acceptable was the procedure performed today" measured on a 100 mm visual analog scale
  - Continuous variable ranging from 0 to 100
- Patient's response to "overall, how would you rate the experience of your biopsy procedure today" measured on a 100 mm visual analog scale
  - Continuous variable ranging from 0 to 100
- Provider's response to "overall, how well did the subject tolerate the procedure today" measured on a 100 mm visual analog scale
  - Continuous variable ranging from 0 to 100
- Provider's response to "overall, how satisfied are you with the procedure performed today" measured on a 100 mm visual analog scale
  - Continuous variable ranging from 0 to 100

#### Data

 Subjects were recruited from patients visiting the Duke Cancer Center Gynecology Oncology Clinic for a vulvar biopsy. Patients were approached by the provider and asked about interest in participating in the study. If interested, research personnel then discussed the study with the patient. Informed consent was done via an electronic consent form. Enrollment log, study questionnaires, and pain assessment forms were all stored in REDCap. All exported copies are saved on secure Duke password protected servers. Randomization to a treatment arm was done using the randomization tool in REDCap. Data were exported from REDCap on March 13, 2019 by [name] and stored on the BERD Method Core's shared drive.

#### **Inclusion Criteria**

- Females above 18 years old presenting to Duke Gynecology Oncology Clinic for vulvar biopsy
- Able to provide informed consent in English and agree to the risks of the study

#### **Exclusion Criteria**

- Not able to provide informed consent
- Vulvar biopsy on hair bearing surface

# Analysis Objectives

1. Objective: Describe patient characteristics in the analysis cohort by treatment arm and overall

**Analysis:** Create a baseline table of patient characteristics by treatment arm and overall. Continuous variables will be summarized with mean (SD), median (25th percentile, 75th percentile), and range. Categorical variables will be reported as frequency and percent. This table can be used to check that randomization approximately distributed confounders equally between the two treatment arms. P values will not be provided.

**Conclusions:** All pre-procedure data are presented in Table 1.1. There was a total of 37 enrolled patients, with 19 and 18 in the EMLA cream and lidocaine injection group, respectively.

Table 1.1. Pat	ient demographics and cha	racteristics	
	EMLA cream Li	docaine injection only	Total
	(N=19)	(N=18)	(N=37)
Generalized Anxiety Disorder 7-Item 8	Scale: Over the last 2 weeks	, how often have you	been bothered
by	y the following problems?	-	
1. Feeling nervous, anxious, or on edge			
Not at all sure	8 (42.1%)	10 (55.6%)	18 (48.6%)
Several days	7 (36.8%)	5 (27.8%)	12 (32.4%)
Over half the days	2 (10.5%)	1 (5.6%)	3 (8.1%)
Nearly every day	2 (10.5%)	2 (11.1%)	4 (10.8%)
2. Not being able to stop or control wor	rrying		
Not at all sure	13 (68.4%)	13 (72.2%)	26 (70.3%)
Several days	5 (26.3%)	3 (16.7%)	8 (21.6%)
Nearly every day	1 (5.3%)	2 (11.1%)	3 (8.1%)

	EMLA cream Li (N=19)	idocaine injection only (N=18)	Total (N=37)
3. Worrying too much about different things			( )
Not at all sure	13 (68.4%)	7 (38.9%)	20 (54.1%)
Several days	3 (15.8%)	7 (38.9%)	10 (27.0%)
Over half the days	1 (5.3%)	2 (11.1%)	3 (8.1%)
Nearly every day	2 (10.5%)	2 (11.1%)	4 (10.8%)
4. Trouble relaxing			
Not at all sure	13 (68.4%)	6 (33.3%)	19 (51.4%)
Several days	4 (21.1%)	8 (44.4%)	12 (32.4%)
Over half the days	1 (5.3%)	1 (5.6%)	2 (5.4%)
Nearly every day	1 (5.3%)	3 (16.7%)	4 (10.8%)
5. Being so restless that it's hard to sit still			
Not at all sure	16 (84.2%)	12 (66.7%)	28 (75.7%)
Several days	1 (5.3%)	4 (22.2%)	5 (13.5%)
Over half the days	1 (5.3%)	1 (5.6%)	2 (5.4%)
Nearly every day	1 (5.3%)	1 (5.6%)	2 (5.4%)
6. Becoming easily annoyed or irritable			
Not at all sure	14 (73.7%)	9 (50.0%)	23 (62.2%)
Several days	5 (26.3%)	8 (44.4%)	13 (35.1%)
Nearly every day	0 (0.0%)	1 (5.6%)	1 (2.7%)
7. Feeling afraid as if something awful might			
happen			
Missing	1 (.%)	0 (.%)	1
Not at all sure	14 (77.8%)	14 (77.8%)	28 (77.8%)
Several days	3 (16.7%)	4 (22.2%)	7 (19.4%)
Nearly every day	1 (5.6%)	0 (0.0%)	1 (2.8%)
Tot	tal scores		
Total - Not at all sure	10	10	25
N	19	18	37
Mean (SD)	0.0 (0.0)	0.0 (0.0)	0.0 (0.0)
Median	0.0	0.0	0.0
Q1, Q3	0.0, 0.0	0.0, 0.0	0.0, 0.0
Range	(0.0-0.0)	(0.0-0.0)	(0.0-0.0)
Total - Several days			
N	19	18	37
Mean (SD)	1.5 (1.5)	2.2 (1.5)	1.8 (1.5)
Median	1.0	2.0	2.0
Q1, Q3	0.0, 3.0	1.0, 3.0	1.0, 3.0
Range	(0.0-5.0)	(0.0-5.0)	(0.0-5.0)

# Table 1.1. Patient demographics and characteristics

	EMLA cream L (N=19)	idocaine injection only (N=18)	Total (N=37)
Total - Over half the days	10	10	25
N (CD)	19	18	37
Mean (SD)	0.5 (1.5)	0.6 (1.3)	0.5 (1.4)
Median	0.0	0.0	0.0
Q1, Q3	0.0, 0.0	0.0, 0.0	0.0, 0.0
Range	(0.0-6.0)	(0.0-4.0)	(0.0-6.0)
Total - Nearly every day			
Ν	19	18	37
Mean (SD)	1.3 (3.5)	1.8 (3.6)	1.5 (3.5)
Median	0.0	0.0	0.0
Q1, Q3	0.0, 0.0	0.0, 3.0	0.0, 0.0
Range	(0.0-15.0)	(0.0-12.0)	(0.0-15.0)
Total Score			
N	19	18	37
Mean (SD)	3.3 (4.0)	4.6 (4.2)	3.9 (4.1)
Median	1.0	3.5	2.0
Q1, Q3	0.0, 5.0	2.0, 8.0	1.0, 7.0
Range	(0.0-15.0)	(0.0-15.0)	(0.0-15.0)
If you checked off any problems, how difficult have these made it for you to do your work, take			
care of things at home, or get along with other			
people?			
Missing	1 (.%)	0 (.%)	1
Not difficult at all	14 (77.8%)	14 (77.8%)	28 (77.8%)
Somewhat difficult	4 (22.2%)	3 (16.7%)	7 (19.4%)
Extremely difficult	0 (0.0%)	1 (5.6%)	1 (2.8%)
A.g.o.			
Age N	19	18	37
Mean (SD)	57.9 (16.3)	58.7 (10.8)	58.3 (13.7)
Median	60.0	58.5	60.0
Q1, Q3	46.0, 74.0	51.0, 65.0	51.0, 66.0
Range	(27.0-81.0)	(40.0-78.0)	(27.0-81.0)
5	× ,		· · · · ·
Race			
Black or African American	7 (36.8%)	9 (50.0%)	16 (43.2%)
White or Caucasian	12 (63.2%)	9 (50.0%)	21 (56.8%)
Ethnicity			
Not Hispanic	18 (94.7%)	18 (100.0%)	36 (97.3%)

# Table 1.1. Patient demographics and characteristics

	EMLA cream (N=19)	Lidocaine injection only (N=18)	Total (N=37)
Hispanic	1 (5.3%)	0 (0.0%)	1 (2.7%)
Highest level of education			
Less than a high school diploma	0 (0.0%)	2 (11.1%)	2 (5.4%)
High school degree or equivalent (GED)	5 (26.3%)	4 (22.2%)	9 (24.3%)
Some college	9 (47.4%)	7 (38.9%)	16 (43.2%)
Graduated college	3 (15.8%)	5 (27.8%)	8 (21.6%)
Post graduate degree	2 (10.5%)	0 (0.0%)	2 (5.4%)
Prior vulvar biopsy	16 (84.2%)	17 (94.4%)	33 (89.2%)
Number of prior vulvar biopsies			
Ν	16	17	33
Mean (SD)	3.2 (4.6)	1.8 (1.0)	2.5 (3.3)
Median	2.0	1.0	2.0
Q1, Q3	1.0, 3.0	1.0, 3.0	1.0, 3.0
Range	(1.0-20.0)	(1.0-4.0)	(1.0-20.0)
Takes any prescription medication for pain	5 (26.3%)	3 (16.7%)	8 (21.6%)
Takes any prescription medication for nerves or anxiety	2 (10.5%)	5 (29.4%)	7 (19.4%)
Missing	0	1	1
Baseline vulva pain (mm)			
Ν	19	18	37
Mean (SD)	7.7 (21.4)	2.4 (4.5)	5.1 (15.7)
Median	0.0	0.0	0.0
Q1, Q3	0.0, 5.0	0.0, 3.0	0.0, 3.0
Range	(0.0-92.0)	(0.0-17.0)	(0.0-92.0)
Baseline anxiety level (mm)			
Ν	19	18	37
Mean (SD)	21.8 (21.5)	38.1 (29.3)	29.7 (26.5)
Median	19.0	31.5	21.0
Q1, Q3	0.0, 31.0	12.0, 61.0	8.0, 48.0
Range	(0.0-65.0)	(0.0-91.0)	(0.0-91.0)

# Table 1.1. Patient demographics and characteristics

2. Objective: Compare highest subjective pain score between patients receiving EMLA cream vs. lidocaine

**Analysis:** Linear regression will be used to test if the highest pain score differs between treatment arms, controlling for baseline pain. The regression coefficient, 95% confidence interval, and p value will be reported for the treatment effect. A significant p value would indicate that the highest pain score, on average, differed between the two treatment arms. If there is not a significant difference between treatment arms with regards to the highest pain score, then the mean and variance estimates from these patients will be used to recalculate the sample size needed (objective 3).

**Conclusions:** The highest pain score was created as the maximum between pain during application of anesthesia and pain immediately following biopsy. The median highest pain score in the EMLA cream group was 20.0 mm vs. 56.5 mm in the lidocaine injection group.

Table 2.1. Highest pain score by treatment arm					
	EMLA cream (N=19)	Lidocaine injection only (N=18)	Total (N=37)		
Highest pain score (n	nm)				
Ν	19	18	37		
Mean (SD)	26.7 (29.0)	52.5 (32.0)	39.2 (32.8)		
Median	20.0	56.5	27.0		
Q1, Q3	5.0, 50.0	26.0, 80.0	12.0, 61.0		
Range	(0.0-100.0)	(5.0-100.0)	(0.0-100.0)		

All patients in the lidocaine injection group reported having the same as or more pain during the injection than the biopsy. Four out of nineteen patients in the EMLA cream group reported more pain from the application of the cream than the biopsy, and three reported the same amount of pain.

Frequency Row Percent	More pain from biopsy	Same amount of pain	More pain from application of anesthesia	Total
Lidocaine injection only	0 0.00	1 5.56	17 94.44	18
EMLA cream	12 63.16	3 15.79	4 21.05	19
Total	12	4	21	37

From the linear regression model, patients that received EMLA cream were expected to report their highest pain score 25.7 mm lower than the lidocaine injection group (95% CI = [-45.1, -6.3], p < 0.01). In other words, the highest pain score in the EMLA cream group was significantly lower than in the lidocaine injection group.

**3. Objective:** Calculate the new sample size needed using effect estimates from the interim analysis

**Analysis:** Using the difference in means between groups and the estimate of the standard deviation, the sample size needed to detect the observed difference in pain scores between the two treatment arms at 90% power with an alpha level of 0.05 using a two-sample t-test will be calculated. This will be the number of patients that will need to be NEWLY accrued. The current patients do not count towards this sample size.

**Conclusions:** Since the highest pain score was significantly lower in the EMLA cream group compared to the lidocaine group, the trial does not need to continue.

4. Objective: Compare secondary and exploratory outcomes between treatment arms

**Analysis:** The secondary objective, pain at vulvar biopsy, will be compared between treatment arms using linear regression, controlling for baseline pain, similar to the primary objective. The exploratory objectives, excluding provider's response to "overall, how satisfied were you with the procedure," will be compared between treatment arms using Wilcoxon rank sum test. A significant p value would mean that one of the treatment arms tended to have higher scores on the VAS than the other. Since the same providers are rating their satisfaction with the procedure multiple times, the responses will be correlated. To take this into account, provider procedure satisfaction scores will be compared between treatment arms using generalized estimating equations (GEE) assuming a normal distribution. The working correlation matrix will be chosen using QIC and the robust variance estimator will be used.

**Conclusions:** There was not a significant difference between treatment arms with regards to pain at biopsy (EMLA cream  $\beta$  = 6.9; 95% confidence interval [-12.0, 25.9]; p = 0.47). Patients that were randomized to EMLA cream had a significantly better experience with the procedure than those that received lidocaine (p = 0.02). There was not a significant difference between treatment arms for patient acceptability or provider's perception of subject tolerance (p = 0.06 for both). A compound symmetric working correlation structure was used for the marginal model comparing provider satisfaction scores between treatment groups. There was not a significant difference between treatment treatment arms for provider satisfaction scores (p = 0.35). As a note, do not place too much emphasis on the insignificant results as this is still a small sample size and the trial was not powered for these objectives. A lack of statistical significance does not prove that there is no difference. Summary statistics for the secondary and exploratory objectives are shown in table 4.1. A lower score indicates better results for all outcomes.

	EMLA cream L (N=19)	idocaine injection only (N=18)	Total (N=37)	P value
Pain at vulvar biopsy (mm)				0.47
Ν	19	18	37	
Mean (SD)	24.1 (30.3)	17.4 (29.1)	20.8 (29.5)	
Median	6.0	3.0	5.0	
Q1, Q3	1.0, 50.0	0.0, 15.0	0.0, 26.0	
Range	(0.0-100.0)	(0.0-100.0)	(0.0-100.0)	
Patient's experience with the procedure (lower is				0.02
better)				
Ν	19	18	37	
Mean (SD)	11.2 (23.1)	27.1 (29.7)	18.9 (27.3)	
Median	2.0	17.0	6.0	
Q1, Q3	0.0, 17.0	5.0, 38.0	0.0, 25.0	
Range	(0.0-99.0)	(0.0-100.0)	(0.0-100.0)	
Patient's acceptability of the procedure (lower				0.06
is better)				
Ν	19	18	37	
Mean (SD)	10.8 (21.1)	17.9 (19.8)	14.2 (20.5)	
Median	0.0	10.5	5.0	
Q1, Q3	0.0, 18.0	1.0, 33.0	0.0, 21.0	
Range	(0.0-86.0)	(0.0-67.0)	(0.0-86.0)	
Provider's perception of patient tolerance (lower is better)				0.06
Ν	19	18	37	
Mean (SD)	16.6 (28.7)	20.4 (18.0)	18.5 (23.8)	
Median	3.0	15.0	13.0	
Q1, Q3	0.0, 19.0	9.0, 27.0	0.0, 20.0	
Range	(0.0-99.0)	(0.0-62.0)	(0.0-99.0)	
Provider's satisfaction with the procedure (lower				0.35
is better)				
Ν	19	18	37	
Mean (SD)	21.2 (35.8)	13.1 (13.5)	17.2 (27.3)	
Median	3.0	9.5	7.0	
Q1, Q3	0.0, 18.0	3.0, 18.0	0.0, 18.0	
Range	(0.0-99.0)	(0.0-51.0)	(0.0-99.0)	

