Procedure: The subject will then be placed in dorsal lithotomy position on the Gynecology Oncology pelvic exam tables in preparation for the procedure. If the patient is randomized to the EMLA cream group, the EMLA cream will be applied at the intended site of biopsy and left in place for a minimum of 10 minutes prior to biopsy. Approximately 5 g of EMLA should be applied in a thick layer to the area to be biopsied (a 1g strip is approximately 1.5 x 0.2 inches and squeezed from the tube in a narrow strip) (10). The subject will report a pain score at time of EMLA application. After 10 minutes vulvar biopsy will be performed.

For subjects receiving lidocaine injection, approximately 2 mL of 1% lidocaine will be injected superficially at the planned biopsy site using a 25- or 27-gauge needle at the discretion of the physican. The subject will report pain at time of injection on a 100 mm visual analog scale before proceeding to vulvar biopsy. The provider will then wait at least one minute after lidocaine injection before performing the biopsy.

In both arms, should the provider deem anesthesia to be inadequate prior to performance of the biopsy, an additional lidocaine injection will be allowed prior to biopsy and this will be recorded.

Vulvar biopsies will be performed using standard biopsy forceps or a punch biopsy (3-4 mm) device depending on provider preference. The subject will report pain using a 100 mm visual analog scale immediately following biopsy.

If there are multiple biopsy sites that are treated, and the pain differs between these locations, the highest pain score will be recorded.

If the procedure is interrupted secondary to pain, a pain score will be recorded prior to injecting additional lidocaine, as described above.

Exit Survey: After completion of the procedure, subjects will complete an exit survey, as described above(see appendices), answering questions about overall satisfaction/tolerability of the procedure.

The provider performing the biopsy will also complete a brief survey answering questions about their satisfaction with the procedure and their perception of the acceptability of the procedure performed.

As described above, participants will complete questionnaires electronically with the exception of the pain assessment by visual analog scale, which will be completed on paper and measured distances will be entered into REDCap.

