There is a small risk of topical reaction to the EMLA cream. If irritation does occur, the area of irritation will be cleansed with water and the procedure will be postponed until the irritation is resolved. The subjects will return to clinic to assess for resolution of the area and their indicated vulvar biopsy.

Costs to the Subject

No additional costs will be incurred by the participant as a result of participating in this study

Data Analysis and Statistical Considerations

A 16-mm difference on a standard 100-mm visual analog pain scale was deemed clinically significant. In order to detect a 16-mm difference with 90% power at an alpha level of 0.05 assuming a standard deviation of 25-mm, we estimated a needed sample size of 53 participants in each treatment arm. However, due to time limitations, data collection will end on March 12, 2019. Only patients consented on or prior to March 12, 2019 will be included in the study. Data will be recorded using Research Electronic Data Capture (REDCap), and the database will be locked on March 13, 2019. Pain will be measured during the application of EMLA cream or lidocaine injection, and immediately after biopsy. The primary outcome will be the highest pain score recorded during the procedure. The primary outcome sinclude pain score at vulvar biopsy, patient tolerability and acceptability, and provider's satisfaction with the procedure. All testing will be performed at a two-tailed significance level of 0.05.

If significance for the primary objective is not achieved, then patient accrual will continue based on a new sample size determined by the primary results of this analysis. This will be the number of new patients that need to be enrolled. Outcomes will be assessed again at the point when the final sample size is achieved.

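### The SAP defines the primary outcome as the highest of all recorded pain scores but describes the analysed variable as the maximum of only two

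*SAP*

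**What the plan says.** The SAP's Primary Outcome section names the score at application or injection and the score just after biopsy. It also says that, if anesthesia was inadequate before biopsy, "an additional lidocaine injection was given and pain was recorded prior to the additional injection". It closes with the rule: "The highest of all these pain measurements will be used as the primary outcome".

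The conclusions under Objective 2 (SAP, Analysis Objectives) report how the variable was built: "The highest pain score was created as the maximum between pain during application of anesthesia and pain immediately following biopsy". The cross-table there likewise sorts all 37 patients by application pain against biopsy pain only.

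The protocol's Procedure paragraph has two related rules. Where anesthesia is judged inadequate, "an additional lidocaine injection will be allowed prior to biopsy and this will be recorded". Separately: "If the procedure is interrupted secondary to pain, a pain score will be recorded prior to injecting additional lidocaine, as described above". Its Data Analysis section says "Pain will be measured during the application of EMLA cream or lidocaine injection, and immediately after biopsy" and then "The primary outcome will be the highest pain score recorded during the procedure".

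Under Objective 3, the SAP reasons that because the highest score was significantly lower with EMLA "compared to the lidocaine group, the trial does not need to continue".

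**The concern.** An endpoint defined as a maximum depends on which measurements enter it. A score taken before extra lidocaine records pain at the moment when anesthesia was failing. The later post-biopsy score follows further anesthetic and need not be as high. Leaving out such a score can only lower the patient's value.

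The biopsy side matters most in the EMLA arm, where 12 of 19 patients had more pain from biopsy than from application; in the lidocaine arm, 17 of 18 had more from the injection. Additional lidocaine is allowed in both arms, however, so the direction is not known in advance. Omitted EMLA scores would overstate EMLA's benefit, and omitted lidocaine-arm scores would understate it.

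The significant result on this variable is the stated reason for not continuing, with 37 patients against a planned 53 per arm. It should therefore be traceable to its definition.

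**Working it through.** **1. The two descriptions side by side**

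| Score | SAP, Primary Outcome | SAP, Objective 2 conclusions |
|---|---|---|
| Application or injection | included | included |
| Immediately after biopsy | included | included |
| Before an additional injection | included | not named |

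The interruption score comes from the protocol's Procedure paragraph and is named in neither column. The two definitions give different values only for a patient who (a) had an extra score recorded, (b) had it as the highest, and (c) did not have it entered in one of the two fields. The supplied documents give no count of additional injections or interruptions, not even zero.

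**2. Reproducing the reported contrast**

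Inputs from Table 2.1: EMLA 26.7 (SD 29.0), n = 19; lidocaine 52.5 (SD 32.0), n = 18.

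- Pooled variance = (18 × 29.0² + 17 × 32.0²)/35 = 929.9, so the pooled SD is 30.49.
- SE = 30.49 × √(1/19 + 1/18) = 10.03.
- Difference = 26.7 - 52.5 = -25.8 mm; 95% CI -46.2 to -5.4; p = 0.0145 on 35 df.

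This is close to the SAP's adjusted estimate of -25.7 (-45.1 to -6.3), whose half-width is (45.1 - 6.3)/2 = 19.4. The adjusted model cannot be rerun without patient-level baseline pain.

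**3. Approximating the adjusted interval after an assumed change**

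For each assumed change, update the arm's sum and sum of squares, recompute its mean and SD, and obtain a new unadjusted SE. Shift -25.7 by the change in the mean difference, and multiply 19.4 by (new SE)/10.03.

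Example, one EMLA patient from 0 to 100:

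- Sum: 19 × 26.7 = 507.3 becomes 607.3, so the mean is 31.96.
- Sum of squares: 18 × 29.0² + 19 × 26.7² = 28,682.9 becomes 38,682.9, so the SD is 32.7.
- SE = 10.65, ratio 1.062, half-width 20.6.
- Centre = -25.7 + 100/19 = -20.4; interval -41.0 to +0.2.

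All changes below are assumptions; no such values are in the documents.

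| Assumed change (mm) | New mean (SD) in changed arm | SE ratio | Approximate adjusted difference (95% CI) |
|---|---|---|---|
| None | – | 1.000 | -25.7 (-45.1 to -6.3) |
| One EMLA, 20 to 80 | 29.9 (31.4) | 1.039 | -22.5 (-42.7 to -2.4) |
| One EMLA, 20 to 100 | 30.9 (33.4) | 1.074 | -21.5 (-42.3 to -0.7) |
| One EMLA, 0 to 100 | 32.0 (32.7) | 1.062 | -20.4 (-41.0 to +0.2) |
| Two EMLA, 20 to 70 | 32.0 (31.9) | 1.047 | -20.4 (-40.8 to -0.1) |
| Two EMLA, 20 to 80 | 33.0 (33.3) | 1.072 | -19.4 (-40.2 to +1.4) |
| Two EMLA, 60 to 100 | 30.9 (36.0) | 1.119 | -21.5 (-43.2 to +0.2) |
| One lidocaine, 26 to 100 | 56.6 (33.1) | 1.019 | -29.8 (-49.6 to -10.0) |
| One EMLA 20 to 100 and one lidocaine 26 to 100 | 30.9 (33.4); 56.6 (33.1) | 1.092 | -25.6 (-46.8 to -4.4) |

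The starting values 20, 0 and 26 are the EMLA median, the EMLA minimum and the lidocaine lower quartile; 60 is chosen to show the effect of a high start. Two patients who already score high need smaller rises, because pushing both to the top of the scale also widens the interval.

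**4. Cross-check with the width held fixed**

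For the upper limit of -6.3 to reach zero, EMLA maxima must rise by 6.3 × 19 = 119.7 mm in total. That is more than one patient can supply on a 100-mm scale.

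**The case against.** The strongest reply is that this is a gap in wording and no error is shown. The Objective 2 sentence may be shorthand. The protocol's abstract and its Data Analysis section both describe procedural pain collection as application or injection and then biopsy, with no separate rescue score. The protocol clearly asks for a pain score only when the procedure is interrupted; for anesthesia judged inadequate beforehand, it asks only that the additional injection be recorded. An interruption score may have been entered as the biopsy score, and there may have been no rescues at all. All of this stands as possibility. None of it removes the conflict, because the SAP's own outcome definition includes the extra score and its description of the built variable does not.

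A reader might infer three stronger things that the documents do not support:

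- **That a rescue score was dropped.** No text shows that one existed, or that it was left out.
- **That the error favours EMLA.** Additional lidocaine was allowed in both arms. With one large omitted score in each arm, the approximate difference is -25.6 mm and the interval still excludes zero.
- **That one patient easily overturns the result.** An unadjusted t-test with one EMLA patient moved from 20 to 100 gives p = 0.053. The SAP's primary analysis adjusts for baseline pain, and on that approximate scale the same case still excludes zero (-42.3 to -0.7).

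**Conclusion.** The point holds as an unresolved conflict between the defined primary endpoint and the description of the variable analysed. It should be fixed because the decision not to continue rests on that variable. Confidence is medium: the textual mismatch is plain, while its numerical effect is unknown and may be zero.

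For omissions confined to the EMLA arm, a single score removes significance only at about 0 to 100 mm, and then by 0.2 mm. Two scores starting at the arm median need rises of more than about 50 mm each; about 40 mm each suffices if both patients already stand at 60. Omissions in the lidocaine arm would strengthen the result.

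These sizes rest on assumed values and on scaling the reported interval by an unadjusted SE ratio, so limits within a few tenths of a millimetre of zero should be read as borderline.

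**What to change.** 1. Derive the primary variable in both arms as the maximum of every recorded score, as the SAP's Primary Outcome section says, and correct the Objective 2 description to match. Alternatively, state that no extra score existed, or that any such score was already entered in one of the two fields.
2. If any patient's value changes, rerun the baseline-adjusted primary regression and revisit the Objective 3 statement on not continuing.

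The cost is small: a check or recode of one derived variable, using only scores that were actually recorded, or one clarifying sentence. The downside is that the estimate may move in either direction. No change to the rescue rule is proposed.

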#### **Project Summary**

The current standard at the Duke Cancer Center Gynecology Oncology Clinic is to use a lidocaine injection as local anesthesia prior to vulvar biopsy. The injection itself is not without pain and awaiting the injection frequently induces anxiety in patients. Other studies have examined the use of a topical anesthetic in addition to or in place of injected anesthesia. A previous study has found that EMLA cream is associated with less pain at the time of anesthesia administration, but injection anesthesia resulted in better biopsy pain control. Pain was measured on a 100 mm visual analog scale at the time of anesthesia administration and immediately following biopsy. The purpose of this study is to compare EMLA cream to lidocaine injection for analgesia for vulvar biopsy using the highest recorded pain score during the procedure.

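### The analysed highest pain score is described as the maximum of two scores, while the SAP's own definition also counts a score taken before additional lidocaine

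*SAP*

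**What the plan says.** **Definition.** The SAP's Primary Outcome section names pain during application or injection and pain immediately after biopsy. For inadequate anesthesia before biopsy it adds that "an additional lidocaine injection was given and pain was recorded prior to the additional injection". It then states: "The highest of all these pain measurements will be used as the primary outcome". The SAP's Project Summary describes the comparison as "using the highest recorded pain score during the procedure".

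**Protocol.** Data Analysis and Statistical Considerations says: "The primary outcome will be the highest pain score recorded during the procedure". The Procedure paragraph under Study Procedures covers two situations. If anesthesia seems inadequate beforehand, in either arm, "an additional lidocaine injection will be allowed prior to biopsy and this will be recorded"; this asks for the injection to be recorded and does not explicitly ask for a new score. If pain interrupts the procedure, a score is required: "If the procedure is interrupted secondary to pain, a pain score will be recorded prior to injecting additional lidocaine, as described above".

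**Derivation.** Under Objective 2 of the SAP's Analysis Objectives, the Conclusions paragraph says: "The highest pain score was created as the maximum between pain during application of anesthesia and pain immediately following biopsy". It does not mention a score before additional lidocaine. Neither document reports how many top-ups or interruptions occurred.

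**The concern.** The derivation names two components; the definition names three. The third matters most when rescue works. A patient who hurts, receives extra lidocaine and then has a comfortable biopsy may have her worst pain recorded only in the pre-rescue score. Leaving a value out of a maximum can lower that patient's result or leave it unchanged, but never raise it.

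A dropped EMLA score that exceeded the other two would make the EMLA advantage look too large. A dropped lidocaine score of that kind would make it look too small.

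This variable is the primary outcome, and under Objective 3 its significance is the reason given for not continuing the trial. Rescue cannot be assumed absent: Table 4.1 shows EMLA biopsy pain with an upper quartile of 50 mm and a maximum of 100 mm. Those figures do not show that rescue occurred.

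**Working it through.** **Inputs.** Table 2.1: EMLA n = 19, mean 26.7, SD 29.0; lidocaine n = 18, mean 52.5, SD 32.0. Objective 2 regression, adjusted for baseline pain: -25.7 mm, 95% CI -45.1 to -6.3, p < 0.01. Clinical threshold, from the protocol's statistical section: "A 16-mm difference on a standard 100-mm visual analog pain scale was deemed clinically significant".

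**1. Reproduce the reported result.**
- Unadjusted: pooled SD = sqrt[(18 × 29.0² + 17 × 32.0²)/35] = 30.49. The difference is 26.7 - 52.5 = -25.8 mm, 95% CI -46.2 to -5.4, p = 0.015. This agrees well with the adjusted estimate.
- Adjusted: CI half-width = (45.1 - 6.3)/2 = 19.4. With t(34, 0.975) = 2.032, SE = 19.4/2.032 = 9.55. Then t = 25.7/9.55 = 2.69 and p = 0.011, which is not below 0.01. A normal-based interval implies SE = 19.4/1.96 = 9.90 and a normal p of 0.009, so the printed p may come from a normal reference. I use 9.55 and t(34).

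**2. What a dropped score would do.** The true corrected effect cannot be computed, because no pre-rescue scores or counts are reported. The cases below are assumptions: the named EMLA patients have a higher true maximum, no lidocaine score was missed, and the raised patients have average baseline pain.

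- Estimate = -25.7 + k × d/19, for k EMLA patients each raised by d mm.
- EMLA spread is rebuilt from Table 2.1: sum = 19 × 26.7 = 507.3; sum of squares = 18 × 29.0² + 19 × 26.7² = 28,682.9. Each moved patient changes both.
- Adjusted SE = 9.55 × (new pooled SD/30.49). This scaling is approximate.

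Worked case, one patient from 0 to 100 mm: sum 607.3 and sum of squares 38,682.9, so the EMLA SD is sqrt[(38,682.9 - 607.3²/19)/18] = 32.7. The pooled SD is 32.37 and SE = 9.55 × 32.37/30.49, or about 10.13. The estimate is -25.7 + 100/19 = -20.4, with t = 2.02 and p = 0.052.

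| EMLA patients moved | EMLA SD | SE | Estimate (mm) | p |
|---|---|---|---|---|
| none | 29.0 | 9.55 | -25.7 | 0.011 |
| one, 20 to 60 | 29.9 | 9.69 | -23.6 | 0.020 |
| two, 20 to 50 | 29.8 | 9.66 | -22.5 | 0.026 |
| two, 50 to 70 | 31.4 | 9.92 | -23.6 | 0.023 |
| one, 0 to 100 | 32.7 | 10.13 | -20.4 | 0.052 |
| two, 20 to 80 | 33.3 | 10.23 | -19.4 | 0.067 |

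Holding the SE at 9.55 gives smaller p-values (0.040 for one patient raised by 100 mm, 0.050 for two raised by 60 mm). That is the less realistic case, because moving a patient that far also widens the spread.

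**3. Distance to the clinical threshold.** Bringing the estimate to -16 mm takes (25.7 - 16) × 19 = 184.3 mm of missed EMLA pain in total, for example two patients at 92 mm each.

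**4. The other direction.** One lidocaine score missed by 50 mm offsets 50/18 × 19 = 52.8 mm of missed EMLA pain.

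**The case against.** The strongest reply is that no analysis error is shown. The sentence in question sits in a Conclusions paragraph and may be shorthand; the SAP already contains the right rule. It is also what one would write if no third score existed. Two scores could even satisfy the definition. For a pre-biopsy top-up the protocol asks only that the injection be recorded, so the SAP's pre-injection pain could be the application score already held. An interruption score could have been entered as the biopsy score. The scenarios that cross 0.05 are also demanding: the pre-rescue score must exceed both other scores by a wide margin, in the EMLA arm, with no offset in the lidocaine arm.

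Most of this stands, and it is why the point is minor. What it does not do is close the gap. Neither document says that the sentence is shorthand, that no rescue occurred, or how a rescue score was entered. A reader therefore cannot confirm that the analysed variable follows its definition.

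A reader might infer that painful EMLA scores were left out, that the EMLA advantage is therefore exaggerated, and that the decision not to continue was unsound. The documents support none of this. They report no extra score and no rescue counts, and any omission could have fallen in either arm. Nor does the mismatch between p = 0.011 and the printed p < 0.01 point to a dropped score; a normal reference distribution would account for it.

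**Conclusion.** The concern holds as a mismatch between the stated definition and the stated derivation of the primary outcome. Its numerical effect is unknown and may be zero. If a score was dropped, modest omissions leave the result significant (p about 0.02 to 0.03), with estimates of -22.5 mm or beyond. One extreme EMLA omission, or two large ones, could take p just above 0.05 while the estimate stays near -20 mm. The point estimate is therefore sturdier than the p-value, and it is the p-value that was used to decide against further accrual.

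These sizes rest on assumed scores, an SE inferred from the published interval, an approximate scaling of that SE, and no lidocaine omissions. Severity: minor.

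**What to change.** - **Wording.** In the SAP's Primary Outcome section, make explicit that the maximum includes any score taken before additional lidocaine, whether at a pre-biopsy top-up or at an interruption for pain, in both arms. Under Objective 2, derive the variable by that rule.
- **Check.** Go through the 37 held records (paper pain scales and REDCap) and report top-up and interruption counts by arm.
- **Rerun only if needed.** If any such score exceeds the two already used, rederive the highest pain score, rerun Table 2.1 and the Objective 2 regression, and report the new estimate against both 0 and 16 mm. Otherwise state that none did.

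The cost is a small wording change, a review of 37 existing records and, at most, one rerun of the table and regression. When rescue is given need not change. The downside for the sponsor is that the EMLA advantage may shrink.
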